## Appendix 5      Columbia Suicide Severity Rating Scale (C-SSRS) -- Since Last Visit Version

SUICIDAL IDEATION		Since Last Visit

Ask questions 1 and 2. If both are negative, proceed to "Suicidal Behavior" section. If the answer to question 2 is "yes", ask questions 3, 4 and 5. If the answer to question 1 and/or 2 is "yes", complete "Intensity of Ideation" section below.
		

1. Wish to be Dead Subject endorses thoughts about a wish to be dead or not alive anymore, or wish to fall asleep and not wake up. Have you wished you were dead or wished you could go to sleep and not wake up?
 
If yes, describe:
		Yes    No  

2. Non-Specific Active Suicidal Thoughts General, non-specific thoughts of wanting to end one's life/commit suicide (e.g., "I've thought about killing myself") without thoughts of ways to kill oneself/associated methods, intent, or plan during the assessment period. Have you actually had any thoughts of killing yourself?
 
If yes, describe:
		Yes    No  

3. Active Suicidal Ideation with Any Methods (Not Plan) without Intent to Act Subject endorses thoughts of suicide and has thought of at least one method during the assessment period. This is different than a specific plan with time, place or method details worked out (e.g., thought of method to kill self but not a specific plan). Includes person who would say, "I thought about taking an overdose but I never made a specific plan as to when, where or how I would actually do it...and I would never go through with it." Have you been thinking about how you might do this?
 
If yes, describe:
		Yes    No  

4. Active Suicidal Ideation with Some Intent to Act, without Specific Plan Active suicidal thoughts of killing oneself and subject reports having some intent to act on such thoughts, as opposed to "I have the thoughts but I definitely will not do anything about them." Have you had these thoughts and had some intention of acting on them?
 
If yes, describe:
		Yes    No  

5. Active Suicidal Ideation with Specific Plan and Intent Thoughts of killing oneself with details of plan fully or partially worked out and subject has some intent to carry it out. Have you started to work out or worked out the details of how to kill yourself? Do you intend to carry out this plan?
 
If yes, describe:
		Yes    No  
INTENSITY OF IDEATION		

The following features should be rated with respect to the most severe type of ideation (i.e., 1-5 from above, with 1 being the least severe and 5 being the most severe).
 
Most Severe Ideation: _____
 
Type # (1-5) _____      Description of Ideation _____
		Most Severe

Frequency How many times have you had these thoughts? (1) Less than once a week    (2) Once a week    (3) 2-5 times in week    (4) Daily or almost daily    (5) Many times each day
		_____

Duration When you have the thoughts, how long do they last? (1) Fleeting - few seconds or minutes    (4) 4-8 hours/most of day (2) Less than 1 hour/some of the time    (5) More than 8 hours/persistent or continuous (3) 1-4 hours/a lot of time
		_____

Controllability Could/can you stop thinking about killing yourself or wanting to die if you want to? (1) Easily able to control thoughts    (4) Can control thoughts with a lot of difficulty (2) Can control thoughts with little difficulty    (5) Unable to control thoughts (3) Can control thoughts with some difficulty    (0) Does not attempt to control thoughts
		_____

Deterrents Are there things - anyone or anything (e.g., family, religion, pain of death) - that stopped you from wanting to die or acting on thoughts of committing suicide? (1) Deterrents definitely stopped you from attempting suicide    (4) Deterrents most likely did not stop you (2) Deterrents probably stopped you    (5) Deterrents definitely did not stop you (3) Uncertain if deterrents stopped you    (0) Does not apply
		_____

Reasons for Ideation What sort of reasons did you have for thinking about wanting to die or killing yourself? Was it to end the pain or stop the way you were feeling (in other words you couldn't go on living with this pain or how you were feeling) or was it to get attention, revenge or a reaction from others? Or both? (1) Completely to get attention, revenge or a reaction from others    (4) Mostly to end or stop the pain (you couldn't go on living with the pain or how you were feeling) (2) Mostly to get attention, revenge or a reaction from others    (5) Completely to end or stop the pain (you couldn't go on living with the pain or how you were feeling) (3) Equally to get attention, revenge or a reaction from others and to end/stop the pain    (0) Does not apply
		_____

Version 1/14/09

SUICIDAL BEHAVIOR (Check all that apply, so long as these are separate events; must ask about all types)		Since Last Visit
Actual Attempt: A potentially self-injurious act committed with at least some wish to die, as a result of act. Behavior was in part thought of as method to kill oneself. Intent does not have to be 100%. If there is any intent/desire to die associated with the act, then it can be considered an actual suicide attempt. There does not have to be any injury or harm , just the potential for injury or harm. If person pulls trigger while gun is in mouth but gun is broken so no injury results, this is considered an attempt. Inferring Intent: Even if an individual denies intent/wish to die, it may be inferred clinically from the behavior or circumstances. For example, a highly lethal act that is clearly not an accident so no other intent but suicide can be inferred (e.g., gunshot to head, jumping from window of a high floor/story). Also, if someone denies intent to die, but they thought that what they did could be lethal, intent may be inferred.		  
Have you made a suicide attempt? Have you done anything to harm yourself? Have you done anything dangerous where you could have died? What did you do? Did you _____ as a way to end your life? Did you want to die (even a little) when you _____? Were you trying to end your life when you _____? Or did you think it was possible you could have died from _____?		Total # of Attempts _____
Or did you do it purely for other reasons / without ANY intention of killing yourself (like to relieve stress, feel better, get sympathy, or get something else to happen)? (Self-Injurious Behavior without suicidal intent) If yes, describe:		Yes No  
Has subject engaged in Non-Suicidal Self-Injurious Behavior?		Yes No  
Interrupted Attempt: When the person is interrupted (by an outside circumstance) from starting the potentially self-injurious act (if not for that, actual attempt would have occurred). Overdose: Person has pills in hand but is stopped from ingesting. Once they ingest any pills, this becomes an attempt rather than an interrupted attempt. Shooting: Person has gun pointed toward self, gun is taken away by someone else, or is somehow prevented from pulling trigger. Once they pull the trigger, even if the gun fails to fire, it is an attempt. Jumping: Person is poised to jump, is grabbed and taken down from ledge. Hanging: Person has noose around neck but has not yet started to hang - is stopped from doing so.		Yes No  
Has there been a time when you started to do something to end your life but someone or something stopped you before you actually did anything? If yes, describe:		Total # of interrupted _____
Aborted Attempt: When person begins to take steps toward making a suicide attempt, but stops themselves before they actually have engaged in any self-destructive behavior. Examples are similar to interrupted attempts, except that the individual stops him/herself, instead of being stopped by something else. Has there been a time when you started to do something to try to end your life but you stopped yourself before you actually did anything? If yes, describe:		Yes No  
Preparatory Acts or Behavior: Acts or preparation towards imminently making a suicide attempt. This can include anything beyond a verbalization or thought, such as assembling a specific method (e.g., buying pills, purchasing a gun) or preparing for one's death by suicide (e.g., giving things away, writing a suicide note). Has you taken any steps towards making a suicide attempt or preparing to kill yourself (such as collecting pills, getting a gun, giving valuables away or writing a suicide note)? If yes, describe:		Yes No  
Suicidal Behavior: Suicidal behavior was present during the assessment period?		Yes No  
Suicide:		Yes No  
Answer for Actual Attempts Only		Most Lethal Attempt Date:
Actual Lethality/Medical Damage: 0. No physical damage or very minor physical damage (e.g., surface scratches). 1. Minor physical damage (e.g., lethargic speech; first-degree burns; mild bleeding; sprains). 2. Moderate physical damage; medical attention needed (e.g., conscious but sleepy, somewhat responsive; second-degree burns; bleeding of major vessel). 3. Moderately severe physical damage; medical hospitalization and likely intensive care required (e.g., comatose with reflexes intact; third-degree burns less than 20% of body; extensive blood loss but can recover; major fractures). 4. Severe physical damage; medical hospitalization with intensive care required (e.g., comatose without reflexes; third-degree burns over 20% of body; extensive blood loss with unstable vital signs; major damage to a vital area). 5. Death		Enter Code _____
Potential Lethality: Only Answer if Actual Lethality=0 Likely lethality of actual attempt if no medical damage (the following examples, while having no actual medical damage, had potential for very serious lethality: put gun in mouth and pulled the trigger but gun fails to fire so no medical damage; laying on train tracks with oncoming train but pulled away before run over).		Enter Code _____
0 = Behavior not likely to result in injury 1 = Behavior likely to result in injury but not likely to cause death 2 = Behavior likely to result in death despite available medical care		

## Appendix 6      Injection Site Grading Scale

Injection site Reactions	None (Grade 0)	Mild (Grade 1)	Moderate (Grade 2)	Severe (Grade 3)	Potentially Life Threatening (Grade 4)
Pain	None	Does not interfere with activity	Repeated use of non-narcotic pain reliever > 24 hours or interferes with activity	Any use of narcotic pain reliever or prevents daily activity	Emergency room (ER) visit or hospitalization
Tenderness	None	Mild discomfort to touch.	Discomfort with movement.	Significant discomfort at rest	ER visit or hospitalization
Erythema/ Redness* (quantitative)	None	2.5 – 5 cm	5.1 – 10 cm	> 10 cm	Necrosis or exfoliative dermatitis
Induration **	None	2.5 – 5 cm and does not interfere with activity	5.1 – 10 cm or interferes with activity	> 10 cm or prevents daily activity	Necrosis
Swelling ** (subjective)	None	2.5 – 5 cm and does not interfere with activity	5.1 – 10 cm or interferes with activity	> 10 cm or prevents daily activity	Necrosis

\* In addition to grading the measured local reaction at the greatest single diameter, the measurement should be recorded as a continuous variable.

\*\* Induration/Swelling should be evaluated and graded using the functional scale as well as the actual measurement.

Modified from:

U.S. Department of Health and Human Services, Food and Drug Administration, Center for Biologics Evaluation and Research, September 2007. Guidance for Industry: Toxicity Grading Scale for Healthy Adult and Adolescent Volunteers Enrolled in Preventive Vaccine Clinical Trials. [pdf] Available at:

<http://www.fda.gov/downloads/BiologicsBloodVaccines/GuidanceComplianceRegulatoryInformation/Guidances/Vaccines/ucm091977.pdf>. Accessed 30 September 2016.

## Appendix 7      **Injection Site Pain Visual Analog Scale**

How would you rate your injection site pain today?

No Pain \_\_\_\_\_

Pain as bad  
as it could be

Please answer the following question by checking the box with either a “Yes” or “No”:  
Are you currently experiencing any burning or stinging at the injection site?

YES     

NO     

---

Note: Copies of any pre-printed VAS forms to be completed by a subject must be checked to confirm that the rating scale measures 100 mm (3.94 in) in length.

## **Appendix 8      Elevated Liver Function Tests**

Elevated liver functions tests meeting one of the following criteria below must follow the outlined procedures.

### **Criteria 1**

**ALT  $\geq$ 3X ULN and  $<$ 5X ULN**  
**+ Bilirubin  $<$ 2X ULN**  
**+ DO NOT exhibit hepatitis symptoms or rash**

- Contact the Indivior Medical Monitor within 24 hours of learning of the abnormality to discuss subject safety.
- Subject may continue study treatment, if liver chemistries (ALT, AST, alkaline phosphatase, bilirubin) can be monitored weekly for up to 4 weeks.
- If the subject later meets criteria 2 or 3, immediately withdraw study treatment, perform additional testing and continue safety follow-up until liver chemistries resolve, stabilize or return to baseline values.
- After 4 weeks of monitoring, if ALT  $<$ 3XULN and bilirubin  $<$ 2XULN, subject must be monitored twice monthly until liver chemistries normalize or return to within baseline values.

### **Criteria 2**

**ALT  $\geq$ 5X ULN**  
**or**  
**ALT  $\geq$ 3X ULN**  
**+ Hepatitis symptoms or rash**  
**+ cannot be monitoring for 4 weeks or have elevations that persist  $\geq$ 4 weeks**

- Subject must not receive any further injections of RBP-6000.
- Contact the Indivior Medical Monitor within 24 hours of learning of the abnormality to discuss subject safety and any addition laboratory testing required.
- Make every reasonable attempt to have the subject return to the clinic within 24-72 hours for repeat liver chemistries and additional testing.
- Monitor subject weekly until liver chemistries (ALT, AST, alkaline phosphatase, bilirubin) resolve, stabilize or return to within baseline values.

- Upon completion of the safety follow-up, the subject must be withdrawn from the study unless further follow-up is required.

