## **6.5 Clinical Laboratory Tests**

### **6.5.1 Laboratory Parameters**

All clinical laboratory assessments will be performed by a clinical laboratory accredited by the College of American Pathologists or with a Certificate of Compliance or Accreditation (or Certificate of Waiver for CLIA-waived tests) issued by the Center for Medicare & Medicaid Services. The laboratory assessments will include routine and screening laboratory tests.

See the SOE in [Appendix 1](#) for the timing of the specific required laboratory tests which are listed in [Table 2](#).

Any abnormal hematology, chemistry, or urinalysis test result deemed clinically significant by the Investigator will be repeated. For any test abnormality deemed clinically significant, an AE will be recorded (unless the result was considered erroneous) and repeat analysis will be performed until resolution or until the Investigator determines that resolution of the laboratory abnormality is not expected.

Subjects will be in a seated or supine position during blood collection. Clinical laboratory panels are listed in [Table 2](#).

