#### **6.9.3 Performing Adverse Events Assessments**

The Investigator is ultimately responsible for assessing and reporting all AEs as outlined in the protocol. The assessment of AEs may be delegated to a medically qualified Sub-investigator, trained on this study protocol, who is listed on the FDA Form 1572 or equivalent document, and on the delegation of authority form.

AEs should be volunteered by the subject or solicited from the subject using a standard statement, obtained from examination of the subject at a site visit, or from observations of clinically significant laboratory values or special examination abnormal values. If an event assessed by one of the study scales requires intervention, or if in the opinion of the Investigator, it is clinically significant, then it will be reported as an AE. Any ongoing AEs reported in the RB-US-13-0003 study will be recorded in the eCRF for this study.

All AEs are to be assessed and recorded in a timely manner and followed to resolution or until the Investigator determines that there is not an anticipated resolution. Each AE is to be documented with reference to severity, date of occurrence, duration, treatment, and outcome. Furthermore, each AE is to be classified as being serious or non-serious. In addition, the Investigator must assess whether the AE is drug-related or not.

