**ALT  $\geq$ 3X ULN + INR >1.5:**

Note: INR testing is not required per protocol and the threshold value does not apply to subjects receiving anticoagulants.

- Subject must not receive any further injections of RBP-6000.
- Contact the Indivior Medical Monitor within 24 hours of learning of the abnormality to discuss subject safety and any addition laboratory testing required.
- Make every reasonable attempt to have the subject return to the clinic within 24 hours for repeat liver chemistries, additional testing and close monitoring (with specialist or hepatology consultation recommended).
- Monitor the subject twice weekly until liver chemistries (ALT, AST, alkaline phosphatase, bilirubin) resolve, stabilize or return to within baseline values.
- Upon completion of the safety follow-up, the subject must be withdrawn from the study unless further follow-up is required.

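### Protocol Appendix 8, Criteria 2: read as AND, the plus signs leave a symptomatic, monitorable subject with ALT 3 to <5× ULN, bilirubin <2× ULN, under 4 weeks' elevation and INR not >1.5 (or unmeasured) outside every liver criterion

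*Protocol*

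**What the plan says.** Protocol Appendix 8 is binding on any subject who meets a criterion: "Elevated liver functions tests meeting one of the following criteria below must follow the outlined procedures".

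- **Criteria 1** joins three conditions with plus signs: ALT from 3× to below 5× ULN, bilirubin below 2× ULN, and subjects who "DO NOT exhibit hepatitis symptoms or rash". It requires Medical Monitor contact within 24 hours and then says: "Subject may continue study treatment, if liver chemistries (ALT, AST, alkaline phosphatase, bilirubin) can be monitored weekly for up to 4 weeks". The step that opens "After 4 weeks of monitoring, if ALT" covers only subjects whose ALT has fallen below 3× ULN and whose bilirubin is below 2× ULN.
- **Criteria 2** is either ALT ≥5× ULN, or a second limb of three lines joined by plus signs: ALT ≥3× ULN; hepatitis symptoms or rash; and "cannot be monitoring for 4 weeks or have elevations that persist" 4 weeks or more. It stops all further injections. It also requires Medical Monitor contact within 24 hours, an attempt to bring the subject back within 24 to 72 hours, and weekly chemistries.
- **Criteria 3** is ALT ≥3× ULN plus bilirubin ≥2× ULN (over 35% direct), or ALT ≥3× ULN plus INR >1.5. A note adds that "INR testing is not required per protocol".

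**The concern.** In Criteria 1 and 3 the plus sign can only mean that every condition must hold. Where Appendix 8 wants alternatives between limbs, it writes the word *or*. Nothing gives the plus sign another meaning in Criteria 2, and Protocol 6.5.4, 6.9.9 and 6.12.2 only point back to the appendix.

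A site that applies the same convention would stop a symptomatic subject with ALT 3 to <5× ULN under Criteria 2 only if that subject also cannot be monitored or has had the elevation for at least 4 weeks. The result is perverse. The subject with symptoms has nothing mandated, while an asymptomatic subject with identical laboratory values has mandatory 24-hour contact and may continue only with weekly chemistries. A subject who starts in Criteria 1 and then develops symptoms would likewise leave Criteria 1 without reaching Criteria 2.

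What is at stake is an explicit stop rule for possible liver injury with a monthly depot. No estimate or test is affected.

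**Working it through.** **Step 1. Classify subjects under each reading.** The scope is ALT 3 to <5× ULN, bilirubin <2× ULN and INR not >1.5 or not measured, so Criteria 3 is never met. The right-hand column reads the last three conditions of Criteria 2 as alternatives, each combined with ALT ≥3× ULN.

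| Symptoms or rash | Can be monitored | Lasted ≥4 weeks | Plus sign as AND | Explicit alternatives |
|---|---|---|---|---|
| No | Yes | No | Criteria 1 | Criteria 1 |
| No | No | Either | Criteria 1, permission to continue withheld | Criteria 2, stop |
| No | Yes | Yes | Criteria 1, no stated action while ALT stays ≥3× | Criteria 2, stop |
| **Yes** | **Yes** | **No** | **None** | **Criteria 2, stop** |
| Yes | No | Either | Criteria 2, stop | Criteria 2, stop |
| Yes | Yes | Yes | Criteria 2, stop | Criteria 2, stop |

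The bold row is the gap. Symptoms rule out Criteria 1, and the third line of Criteria 2 is not met. If the final *or* in Criteria 2 is grouped more loosely, so that persistence stands alone as a trigger, the bold row still meets no criterion. The third row would then reach Criteria 2, so the remark on that row depends on the tighter grouping.

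**Step 2. Limits of the gap.** For symptomatic, monitorable subjects with ALT 3 to <5× ULN, cross three bilirubin states (<2×; ≥2× with ≤35% direct; ≥2× with >35% direct) with two INR states and two durations: 3 × 2 × 2 = 12 combinations. Under AND, 10 of the 12 meet a criterion. All 6 persistent ones meet Criteria 2. Of the 6 not persistent, 3 have INR >1.5 and 1 more has bilirubin ≥2× with >35% direct, so 4 meet Criteria 3. The other 2 are the bold row and its counterpart with bilirubin ≥2× and ≤35% direct. With explicit alternatives all 12 meet Criteria 2. These are combinations, not frequencies.

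**Step 3. Injections before the AND stop.** Let R be the day of the first abnormal sample and K ≥ R the day its result is known. Persistence is counted from R. The AND stop then cannot apply before R + 28, so the days at issue run from K to R + 27. Spacing is nominally 28 days, allowed range 26 to 35 (Protocol 5.3).

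- *Nominal spacing.* While dosing continues, exactly one dosing day falls in R to R + 27. It is a further injection if it comes after the result is known (count 1), and not otherwise (count 0).
- *Allowed window.* Two doses at d and d + g, with g ≥ 26, need d ≥ K and d + g ≤ R + 27, so d ≤ R + 1. The only pairs are (R, R + 26), (R, R + 27) and (R + 1, R + 27), and the result must be known before the first dose of the pair. None is also possible, for example doses on R − 1 and R + 28 (gap 29). The range is 0 to 2.
- *Explicit alternatives.* 0 once the result and the symptoms are known.

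**Step 4. Which samples matter.** Chemistry is scheduled only at screening and at EOS/ET (Protocol 9.5.1.2 and Appendix 1).

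- *Screening.* R is Day 1, the day of injection 1. Then R + 28 = Day 29, the nominal day of injection 2. If the result is not known before injection 1, the AND reading adds 0 at nominal spacing. Injection 2 is allowed on Days 27 to 36 (1 + 26 to 1 + 35) and precedes the stop only on Day 27 or 28.
- *EOS/ET.* No injections remain, so 0.

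At nominal spacing the exposure therefore comes from ad hoc tests between these visits, which Protocol 3.1 allows for examining adverse events.

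**The case against.** The best counter-argument is that the intent is clear from context. Each later line of the second limb is the failure of a condition for continuing under Criteria 1, and the 4-week terms match. Alternatives were very probably meant. That stands, and it makes this a drafting ambiguity. It does not close the gap, because a mandatory stop rule should not depend on sites inferring it. Lost page layout cannot be wholly excluded, but the plus signs survive in the text.

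Other safeguards also remain. Protocol 5.3 lets a dose be delayed within the window for a safety concern. Protocol 6.5.1 says: "Any abnormal hematology, chemistry, or urinalysis test result deemed clinically significant by the Investigator will be repeated". Protocol 6.9.3 says: "All AEs are to be assessed and recorded in a timely manner and followed to resolution", or until no resolution is anticipated. Protocol 6.5.4 and 6.9.9 call for careful assessment of liver values above 3× ULN. Protocol 6.12 allows withdrawal, and 6.12.2 requires Sponsor contact if continued dosing appears unsafe. All of these soften the gap, but they turn on judgement and none mandates a stop for this subject.

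A reader might infer more than the documents support:

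- *That every symptomatic, monitorable subject with ALT 3 to <5× ULN escapes.* Persistence of 4 weeks, INR >1.5, or bilirubin ≥2× with over 35% direct brings the subject into Criteria 2 or 3.
- *That the protocol authorises continued dosing of this subject.* Within Appendix 8, only Criteria 1 gives permission to continue, and only without symptoms. What is missing is an explicit stop and its procedures.
- *That an asymptomatic elevation lasting 4 weeks or more may be dosed through.* The permission is tied to up to 4 weeks of monitoring, and the text is then silent if ALT stays ≥3×. This is silence, so it is only a secondary remark.
- *That the AND reading always costs one extra injection.* A dose given on the sampling day before the result is known would be given under either reading.

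**Conclusion.** The point holds for one defined profile: ALT 3 to <5× ULN, bilirubin <2× ULN, hepatitis symptoms or rash, monitorable, elevation under 4 weeks, INR not >1.5 or not measured. Under the literal AND reading this subject meets no criterion and loses the mandated stop, contact, return visit and weekly schedule.

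The size is modest. The documents give no frequency and show no such subject. Counted from when the result is known, the difference is 0 or 1 injection at nominal spacing, and 2 only at the short end of the window with a result known almost at once. This rests on three assumptions: persistence is counted from the first abnormal sample, retesting takes place, and ALT stays ≥3× ULN. If ALT falls below 3× before 4 weeks, the AND stop is never triggered. Laboratory turnaround is not stated, so the split between 0 and 1 cannot be fixed. It is worth correcting because the rule protects subjects and the correction is small.

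**What to change.** Rewrite Criteria 2 so that ALT ≥3× ULN is attached to each alternative:

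- ALT ≥5× ULN; OR
- ALT ≥3× ULN with hepatitis symptoms or rash; OR
- ALT ≥3× ULN that cannot be monitored weekly for 4 weeks; OR
- ALT ≥3× ULN persisting for 4 weeks or more.

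Simply replacing each plus sign with OR would be wrong: ALT ≥3× ULN alone would become a stop, and Criteria 1 would lose its purpose. The wording above keeps Criteria 1 intact and also settles the persistent asymptomatic case.

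The cost is a wording change through a protocol amendment. Appendix 8 does not define hepatitis symptoms, and Protocol 1.3 lists nausea and vomiting among the common effects of buprenorphine, so some stops may prove unnecessary. They would fall on subjects for whom no other treatment venue has been found (Protocol 2). The Investigator's judgement of the term would decide. No statistical analysis changes: the hepatotoxicity summary in SAP 12.2, Table 5, uses its own thresholds.
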